6.5.5 Supplementary Patient Reported Outcome (PRO) Analysis

As a supplementary PRO analysis, the PRO analysis described in section 6.5.4 will be repeated for change from baseline (month 0) to month 6 (visit 7) in work productivity and work limitation endpoints.

6.6 Secondary Estimand for the Secondary Endpoints

Categorical Weight

The secondary estimand for the categorical weight endpoint of $\geq 5\%$ reduction in body weight from baseline (5% responder) will be assessed using the MMRM for efficacy as described for the secondary estimand for the primary endpoint in section 6.4.3. Analysis will only use assessments from subjects who are adherent to the randomized treatment until end of treatment, or up until the subject is considered non-adherent to the randomized treatment. From the MMRM, individually predicted values for % weight change at month 12 will be used to classify each subject as 5% responder or not. This classification will then be analyzed using a logistic regression model with treatment as the only factor. From the model, the estimated OR (WMP + Rx / WMP) will be presented with the 95% CI and p-value.

PROs

The secondary estimand for change from baseline (month 0) to month 12 (visit 13) in work productivity and work limitation endpoints (section 3.2) will be assessed using the MMRM for efficacy as described for the secondary estimand for the primary endpoint in section 6.4.3. The MMRM for efficacy will only use PRO assessments from subjects who are adherent to the randomized treatment until end of treatment, or up until the subject is considered non-adherent to the randomized treatment. The MMRM for efficacy will be fitted using change in PRO endpoint with randomized treatment as factor and baseline value of the endpoint variable as covariate, all nested within visit. An unstructured covariance matrix for measurements within the same subject will be employed, assuming that measurements for different subjects are independent.

Supplementary PRO Analysis

As a supplementary PRO analysis, the above described PRO analysis will be repeated for change from baseline (month 0) to month 6 (visit 7) in work productivity and work limitation endpoints.

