4.2.6 Randomization

Subjects will be randomized to either WMP + Rx or WMP in a 1:1 ratio via centralized allocation. The study design and subject randomization is depicted in Figure 1.

[figure not shown]

Figure 1. Study design diagram. Subjects will be randomized in a 1:1 manner using centralized allocation to receive WMP + Rx or WMP.

WMP + Rx: Cleveland Clinic’s Integrated Medical Weight Management Program with medication for chronic weight management; WMP: Cleveland Clinic’s Integrated Medical Weight Management Program alone

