6 STATISTICAL METHODS

6.1 Analysis Overview

Subjects will be randomized 1:1 to WMP + Rx or WMP alone. The data analyses for this study will be outlined in further detail in a Statistical Analysis Plan (SAP).

The significance level used in all statistical analyses will be 5% (two-sided).

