6.4.3 Secondary Estimand for the Primary Endpoint

The secondary estimand of the primary endpoint will address the efficacy of medication for chronic weight management if all subjects adhere to their randomized treatment (WMP + Rx or WMP). For the secondary estimand, the primary endpoint will be analyzed using a mixed model for repeated measurements (MMRM) including all subjects, but for subjects considered non-adherent to randomized treatment, only data prior to non-adherence will be used. Month 12 (visit 13) assessments for retrieved drop outs will not be used in this analysis. The MMRM for efficacy will only use assessments from subjects who are adherent to the randomized treatment until end of treatment, or up until the subject is considered non-adherent to the randomized treatment. Subjects in the WMP arm will be considered non-adherent if/when criterion 1 below is met. Subjects in the WMP + Rx arm will be considered non-adherent if/when criterion 1 or 2 is met:

1. Missing 4 SMA visits. In this case, the last assessment made prior to the 4th missed SMA visit will be used as the last assessment. This is also the case if, e.g., 4 SMA visits in a row are missed.
2. Period with no coverage of prescription claims according to PDC exceeds 20% of planned medication duration, or number of days from visit 1 to visit 13. For subjects that drop out early, the expected visit 13 date (derived from the subjects' planned SMA group visit) will be used to calculate planned study duration. The last assessment made prior to exceeding 20% of planned study duration with no prescription claims will be used as last assessment.

The MMRM for efficacy will be fitted using % weight change with randomized treatment as factor and baseline body weight (kg) as covariate, all nested within visit. An unstructured covariance matrix for measurements within the same subject will be employed, assuming that measurements for different subjects are independent.

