6.5.1 Categorical Weight Loss

For the categorical weight loss endpoints ($\geq 5\%$ weight reduction from baseline, $\geq 10\%$ weight reduction from baseline), the proportion of subjects achieving each endpoint will be analyzed using a logistic regression model with treatment as categorical effect and baseline weight (kg) as covariate. From the model, the estimated odds ratio (OR) (WMP + Rx / WMP) will be presented with the 95% CI and p-value. An OR above 1 favors WMP + Rx. Missing weight data will be imputed as described for the primary estimand for the primary endpoint (section 6.4.1).

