5.7.1.1 Categorical Weight Loss

For the categorical weight loss endpoints, subjects will be dichotomized based on body weight loss at month 12 (visit 13) compared to baseline. Analysis will use the imputed weight data derived for the analysis of the primary estimand for the primary endpoint (Section 5.5.1). For the first categorical weight loss endpoint, subjects will be grouped as those with 5% or more body weight loss and those with less than 5% loss. The proportion of subjects achieving the endpoint will be analyzed using a logistic regression model with treatment as categorical effect and baseline weight (kg) as covariate. From the model, the estimated odds ratio (OR) (WMP + Rx / WMP) will be presented, along with the two-sided 95% CI and corresponding p-value. An OR above 1.0 will be interpreted as favoring WMP + Rx. In addition, the predicted probability of achieving at least 5% body weight loss for an average trial subject in each treatment arm will be estimated from the model.

For the second categorical weight loss endpoint, subjects will be dichotomized as those with 10% or more body weight loss and those with less than 10% loss. The analysis will utilize the same approach described for the first categorical weight loss endpoint.

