5.7.2 Statistical Analysis for the Secondary Estimand

5.7.2.1 Categorical Weight Loss

The secondary estimand for the categorical weight endpoint of $\geq 5\%$ reduction in body weight from baseline (5% responder) will be assessed using the MMRM for efficacy as described for the secondary estimand for the primary endpoint in Section 5.6.2. Analysis will only use assessments from subjects who are adherent to the randomized treatment until end of treatment, or up until the subject is considered non-adherent to the randomized treatment. From the MMRM, individually predicted values for % weight change at month 12 will be used to classify each subject as 5% responder or not. This classification will then be analyzed using a logistic regression model with treatment as the only factor. From the model, the estimated OR (WMP + Rx / WMP) will be presented with the 95% CI and p-value. In addition, the predicted probability of achieving at least 5% body weight loss for an average trial subject in each treatment arm will be estimated from the model.

The secondary estimand for the categorical weight endpoint of $\geq 10\%$ reduction of body weight from baseline (10% responder) will follow the same approach outlined for the 5% responder. The estimated OR (WMP + Rx / WMP), 95% CI and p-value will be presented, along with the predicted probability of achieving at least 10% body weight loss for an average trial subject in each treatment arm.

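### The responder odds ratio is adjusted for baseline weight under the primary estimand but not under the secondary estimand: a small model difference that is easy to remove

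*Protocol*

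**What the plan says.** **Primary estimand.** Protocol 6.5.1 analyses the 5% and 10% responder endpoints with a "logistic regression model with treatment as categorical effect and baseline weight (kg) as covariate". SAP 5.7.1.1 has the same model.

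**Secondary estimand.** Baseline weight enters the MMRM, which is "fitted using % weight change with randomized treatment as factor and baseline body weight (kg) as covariate, all nested within visit" (Protocol 6.4.3). From that model, "individually predicted values for % weight change at month 12 will be used to classify each subject as 5% responder or not" (Protocol 6.6). Then: "This classification will then be analyzed using a logistic regression model with treatment as the only factor". SAP 5.7.2.1 repeats this and extends it to the 10% responder; Protocol 6.6 covers only the 5% responder. The SAP also asks this treatment-only model for "the predicted probability of achieving at least 5% body weight loss for an average trial subject in each treatment arm".

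The two documents agree with each other, and neither gives a reason for dropping the covariate. Allocation is 1:1 with no stratification factor stated (Protocol 4.2.6). SAP 3.2 makes all secondary endpoints supportive.

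**The concern.** The two odds ratios will be read side by side as effectiveness and as efficacy under adherence, yet they are different measures. One is conditional on baseline weight and the other is marginal. Odds ratios are not collapsible, so the two models would generally give different answers even with full adherence and complete data, when the estimands coincide.

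The baseline term in the MMRM does not adjust the comparison of classes. The MMRM supplies a predicted value for each subject, and that value carries the subject's own baseline weight. If one arm is heavier by chance, the imbalance passes into the responder counts, and a treatment-only model leaves it there.

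At stake is the reading of a supportive contrast: part of any gap between the two odds ratios could come from the change of model rather than from adherence. The confirmatory test is not touched.

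**Working it through.** **Inputs from the documents.** 100 subjects per arm, a 4-point difference and SD 10 (Protocol 6.3.1); cut-offs of 5% and 10%; two-sided 5% level. The plan gives no figure for the responder odds ratio. Its stated power of 0.80 for the primary comparison reproduces: a two-sample t-test with 100 per arm, difference 4 and SD 10 gives 0.804.

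**Assumed, not in the documents.** Mean WMP loss of 3 to 5%; correlation rho between baseline weight and % change of 0 to 0.5; within-subject correlation of 0.7 where month 12 is predicted.

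**Step 1: marginal odds ratio.** With a WMP mean loss of 3%, the 5% responder probabilities are Φ((3 − 5)/10) = Φ(−0.2) = 0.421 and Φ((7 − 5)/10) = Φ(0.2) = 0.579. The odds ratio is (0.579/0.421)² ≈ 1.9, whatever rho is.

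**Step 2: conditional odds ratio and chance imbalance.** Large-sample logistic fits (400,000 simulated subjects) give the ratios below. The 95% limit for chance imbalance is 1.96 × √(1/100 + 1/100) = 0.277 SD of baseline weight. The last column is exp(0.277 × the baseline-weight coefficient), the factor by which such an imbalance moves the unadjusted odds ratio up or down.

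| rho | OR, treatment only | OR, adjusted | ratio | imbalance factor |
|---|---|---|---|---|
| 0 | 1.90 | 1.90 | 1.000 | 1.00 |
| 0.1 | 1.89 | 1.89 | 1.004 | 1.05 |
| 0.2 | 1.88 | 1.92 | 1.017 | 1.10 |
| 0.3 | 1.92 | 1.99 | 1.040 | 1.15 |
| 0.5 | 1.88 | 2.12 | 1.130 | 1.30 |

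The 10% responder behaves alike (ratios 1.004, 1.015 and 1.037 at rho 0.1, 0.2 and 0.3).

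**Step 3: trials of 100 per arm, complete data.** In 3,000 simulated trials (WMP mean loss 4%), the mean adjusted/unadjusted ratio for the 5% responder was 1.007, 1.018 and 1.044 at rho 0.1, 0.2 and 0.3. With no treatment effect, the treatment-only test rejected in 5.3 to 5.6% of trials. Power changed by about −2 to +1 points for rho up to 0.3; gains of about 6 to 7 points appeared only at 0.5.

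**Step 4: half the subjects predicted.** Month 12 was observed in a random half and otherwise predicted from the repeated-measures model given an earlier weight (1,500 trials per row).

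| rho | median OR, treatment only | median OR, adjusted | 95% range of adjusted/unadjusted in one trial | correlation of unadjusted log OR with imbalance |
|---|---|---|---|---|
| 0 | 2.15 | 2.15 | 0.95–1.09 | −0.01 |
| 0.1 | 2.18 | 2.25 | 0.95–1.14 | −0.06 |
| 0.2 | 2.16 | 2.23 | 0.91–1.23 | −0.10 |
| 0.3 | 2.19 | 2.34 | 0.90–1.39 | −0.22 |
| 0.5 | 2.07 | 2.56 | 0.90–1.78 | −0.37 |

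At rho 0.3 the gap in medians is 2.34/2.19 = 1.07. Once the covariate is added, the correlation with imbalance lies between −0.03 and 0.04. This confirms that the baseline term in the MMRM does not remove imbalance from the class comparison.

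**Step 5: the average-subject probability.** A logistic model with only a two-level treatment term is saturated, so its fitted probability in each arm is the observed arm proportion. Under SAP 5.7.1.1 the same label gives a value that depends on baseline weight.

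**Step 6: what is being predicted.** The MMRM as written has fixed terms and an unstructured covariance matrix, with no subject-level random effect named. If the individual predictions were fixed-effects values, they would have the form a + b × treatment + c × baseline weight. Cutting that at 5% gives a class perfectly separated by treatment and baseline weight, so the adjusted logistic model has no finite estimate. It failed in every simulated trial. The treatment-only model was then estimable in only 21% of trials at rho 0 and 95% at rho 0.3.

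**The case against.** The strongest defence is that both estimands are defined as average effects over all randomized subjects (Protocol 6.1.1). A marginal odds ratio fits that wording at least as well as a conditional one. This stands: a treatment-only model is a legitimate choice, and harmonising in the other direction, with a baseline-standardised marginal measure under both estimands, would also work. It does not explain why the plan uses one kind of odds ratio for one estimand and the other kind for the other.

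A reader might infer that the unadjusted test is biased or has the wrong error rate. The documents do not support that. Randomization leaves no systematic imbalance, chance imbalance is already part of the sampling variance, and Step 3 shows about 5% rejection. That result is for observed classes. Treating predicted classes as if they were data is a separate weakness, and the covariate neither causes nor cures it. The rise in the odds ratio from about 1.9 in Step 2 to about 2.2 in Step 4 likewise comes from predicting month 12, not from the missing covariate.

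A reader might also expect adjustment to bring power, or to make the two odds ratios directly comparable. For rho up to 0.3 there is no material power gain. The analyses would still differ in the data used and in missing-data handling: jump-to-reference imputation against MMRM prediction, with 50% dropout expected. The systematic gap is also small beside sampling error: with a standard error of the log odds ratio of 0.289, the 95% interval spans a factor of exp(1.96 × 0.289) = 1.76 either way.

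**Conclusion.** The point holds as a minor inconsistency. The same responder endpoints are compared with a conditional odds ratio under one estimand and a marginal one under the other, without a stated reason. The unadjusted version retains chance imbalance in baseline weight, and the average-subject wording has no distinct meaning in it.

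The size rests on an assumed correlation. At zero there is nothing to gain. At 0.1 to 0.3 with complete data, the mean gap is about 1 to 5%, rising to about 7% with half the subjects predicted. The ratio in a single trial runs roughly from 0.9 to 1.3, with 1.39 the upper limit in the least favourable of those settings. Larger effects need a correlation near 0.5, for which the documents offer no evidence. Nothing here affects the validity of the treatment-only comparison as such, or the confirmatory conclusion.

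**What to change.** 1. In Protocol 6.6 (5% responder) and SAP 5.7.2.1 (5% and 10% responders), specify logistic regression on treatment and baseline weight in kg, matching Protocol 6.5.1 and SAP 5.7.1.1.
2. In the same places, state that each month 12 prediction conditions on the subject's own observed weights. Without this, a fixed-effects reading makes the adjusted model inestimable.
3. In SAP 5.7.1.1 and 5.7.2.1, define the average-subject probability as the fitted value at the FAS mean baseline weight, under both estimands.

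The cost is a phrase or two in each document and one variable in the model statement. Baseline weight is scheduled at visit 1 for everyone, so no new data are needed. The protocol wording would go through an amendment with IRB review (Protocol 9.1.1). The change should be made before database lock. It removes one model-driven difference between the two odds ratios; the report should still say that others remain.

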6.7 Safety Analysis

SAEs will be collected as described in section 7. No formal safety analyses are planned for this study. SAEs will be coded using Medical Dictionary for Regulatory Activities (MedDRA) and descriptively summarized by System Organ Class (SOC) and Preferred Term (PT).

7 ADVERSE EVENT (AE) REPORTING

7.1 Adverse Events (AEs)

An AE is defined as any untoward medical occurrence in a subject administered a pharmaceutical product or medical device, which does not necessarily have to have a causal relationship to the product or device. Worsening of existing medical conditions, if considered serious and related by the investigator, should be reported as AEs.

For the purposes of this study, AEs will only be required to be collected if they meet the definition of an SAE (section 7.2).

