Safety: For the purposes of this study, adverse events (AEs) will only be required to be collected if they meet the definition of an SAE. Study clinicians are responsible for reporting all SAEs and following the subject until the outcome of the event is closed out. All SAEs will be reported from randomization until EOS at month 12, or until the subject withdraws from the study. Study clinicians are also responsible for recording all pregnancies in female subjects from randomization until EOS at month 12 or subject study withdrawal. The subject will be followed for the duration of the pregnancy until one month post-delivery to report the pregnancy outcome and any AEs or SAEs observed in the fetus or newborn until 1 month of age. Safety will be summarized descriptively.

LIST OF ABBREVIATIONS

Abbreviation	Definition
AE	Adverse Event
ANCOVA	Analysis of Covariance
API	Active Pharmaceutical Ingredient
BMI	Body Mass Index
eCCG	Electronic Case Report Form Completion Guidelines
CFR	Code of Federal Regulations
CI	Confidence Interval
eCRF	Electronic Case Report Form
EDC	Electronic Data Capture
EMR	Electronic Medical Record
EOS	End of Study
FAS	Full Analysis Set
FDA	Food and Drug Administration
FDAAA	Food and Drug Administration Amendment Act
GCP	Good Clinical Practice
GLP-1 RA	Glucagon-Like Peptide-1 Receptor Agonists
HbA1c	Hemoglobin A1c
HIPAA	Health Insurance Portability and Accountability Act
ICF	Informed Consent Form
ICMJE	International Committee of Medical Journal Editors

Abbreviation	Definition
IRB	Institutional Review Board
LSFV	Last Subject First Visit
MedDRA	Medical Dictionary for Regulatory Activities
MMRM	Mixed Model for Repeated Measurements
OR	Odds Ratio
PCD	Primary Completion Date
PCT	Pragmatic Clinical Trial
PDC	Proportion of Days Covered
PO	Per Os
POC	Point of Care
PRO	Patient Reported Outcome
PT	Preferred Term
SAE	Serious Adverse Event
SAP	Statistical Analysis Plan
SC	Subcutaneous
SD	Standard Deviation
SGLT-2	Sodium-Glucose Co-transporter 2
SMA	Shared Medical Appointment
SOC	System Organ Class
US	United States
WLQ-8	Work Limitations Questionnaire 8-Item

Abbreviation	Definition
WMP	Weight Management Program
WPAI:SHP	Work Productivity and Activity Impairment Questionnaire Specific Health Problem

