7.2 Serious Adverse Events (SAEs)

All AEs meeting the definition of SAE will be collected. An SAE is defined as any AE which results in at least one of the following outcomes:

- Initial inpatient hospitalization or prolongation of existing inpatient hospitalization
- A life-threatening event, i.e., an event in which the subject was at immediate risk of dying at the time of the event; not an event that hypothetically could have caused death had it been more severe
- Persistent or significant disability or incapacity
- Congenital anomaly or birth defect in offspring
- Death
- Is deemed serious for any other reason, i.e., if it is an important medical event based on appropriate medical judgement which may jeopardize the subject and may require medical or surgical intervention to prevent one of the other listed outcomes.

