7.2.1 Reporting Period of Serious Adverse Events (SAEs)

SAEs will be reported from randomization until EOS at month 12, or until the subject withdraws from the study. Study clinicians will follow SAEs that occur in any subject during this study in a manner consistent with routine clinical practice.

The study clinician is responsible for alerting Novo Nordisk or its designee to any SAE within 24 hours of becoming aware of it via electronic data capture (EDC) entry. The subject should be followed until the outcome of the event is closed out. Follow-up information should be reported within 24 hours of it becoming available. Requests for follow-up information should be resolved within 14 calendar days.

The study clinician is responsible for assessment of causality and outcome of SAEs, as defined in Appendix 3. Causality and outcome should be provided at the time of reporting an SAE.

If an investigator becomes aware of SAEs after EOS at end of month 12, that are possibly related to the study product, these should be reported as spontaneous events.

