Appendix 3: Causality and Outcome Definitions for Serious Adverse Event (SAE) Reporting

Assessment of Causality

The investigator is obligated to assess the relationship between trial product and the occurrence of each AE/SAE.

Relationship between an AE/SAE and the relevant trial product(s) should be assessed as:

- **Probable:** Good reason and sufficient documentation to assume a causal relationship.
- **Possible:** A causal relationship is conceivable and cannot be dismissed.
- **Unlikely:** The event is most likely related to etiology other than the trial product.

Alternative etiology, such as underlying disease(s), concomitant medication, and other risk factors, as well as the temporal relationship of the event to trial product administration will be considered and investigated.

The investigator should use the individual product information for the assessment. For each AE/SAE, the investigator must document in the medical records that he/she has reviewed the AE/SAE and has provided an assessment of causality.

There may be situations in which an SAE has occurred and the investigator has minimal information to include in the initial report. However, **it is important that the investigator always makes an assessment of causality for every event before the initial transmission of the SAE data.**

The investigator may change his/her opinion of causality in light of follow-up information and send a follow-up report with the updated causality assessment.

The causality assessment is one of the criteria used when determining regulatory reporting requirements.

Final Outcome

The investigator will select the most appropriate outcome:

- **Recovered/resolved:** The subject has fully recovered, or by medical or surgical treatment the condition has returned to the level observed at the first trial-related activity after the subject signed the informed consent.
- **Recovering/resolving:** The condition is improving and the subject is expected to recover from the event. This term is only applicable if the subject has completed the trial or has died from another AE.

- **Recovered/resolved with sequelae:** The subject has recovered from the condition, but with lasting effect due to a disease, injury, treatment or procedure. If a sequelae meets an SAE criterion, the AE must be reported as an SAE.
- **Not recovered/not resolved:** The condition of the subject has not improved and the symptoms are unchanged or the outcome is not known.

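### Protocol 7.1 makes relatedness a condition for reporting a serious worsening of an existing condition, against the all-SAE rules elsewhere; a site that applies it as a filter would under-record such events

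*Protocol*

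**What the plan says.** Protocol 7.1 first defines an AE as an untoward occurrence "which does not necessarily have to have a causal relationship to the product or device". The next sentence deals with pre-existing disease: "Worsening of existing medical conditions, if considered serious and related by the investigator, should be reported as AEs". The section then limits collection to AEs that qualify as serious.

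The collection rules that follow carry no relatedness condition:

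- Synopsis, Safety: "All SAEs will be reported from randomization until EOS at month 12, or until the subject withdraws from the study".
- Protocol 7.2: "All AEs meeting the definition of SAE will be collected". SAP 6.2 repeats this rule.
- Protocol 7.2.1: "Study clinicians will follow SAEs that occur in any subject during this study". The 24-hour alert duty in the same section applies to any SAE.
- Appendix 3: "Relationship between an AE/SAE and the relevant trial product(s) should be assessed as" probable, possible or unlikely. The investigator is to consider "Alternative etiology, such as underlying disease(s), concomitant medication, and other risk factors".

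SAP 6.5 plans a descriptive SAE summary with no formal safety analysis, and SAP 4.1 has statistics presented overall and by arm. The SAP neither repeats nor resolves the 7.1 sentence.

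**The concern.** The sentence names two conditions, serious and related, joined by 'and'. A coordinator deciding whether to enter a hospitalization for worsening asthma that the investigator thinks has nothing to do with treatment could reasonably conclude that 7.1 does not ask for it. The later all-SAE text does not clearly rescue the event, because an SAE is defined in 7.2 as a kind of AE. If 7.1 has kept the event out of the AE set, there is nothing for 7.2 or SAP 6.2 to collect.

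The omission could also differ by arm. The trial is open-label, relatedness is judged by the investigator, and Appendix 3 ties it to the trial product, which WMP subjects do not receive.

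Non-serious AEs are not collected, so apart from pregnancies and technical complaints the SAE table is the trial's adverse event information. An event that was never entered has no causality rating, so the SAE data cannot reveal the gap. SAP 5.4 lists unreported SAEs as a type of major deviation, but it is unclear whether an omitted unrelated worsening would count as one.

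**Working it through.** The plan states no figure on this point, so there is none to reproduce. The check sets the texts side by side and then works out what each reading would record.

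**Texts**

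1. *Is causality needed for an AE?* The definition in 7.1 says no. The worsening sentence in 7.1 says yes, for worsenings. These conflict within one paragraph.
2. *Is causality needed for an SAE to be reported during the study?* The synopsis, 7.2.1 and Appendix 3 say no. An 'unlikely' category is of use only if events judged unlikely are reported.
3. *Where does the protocol plainly restrict by relatedness?* For events the investigator learns of after end of study, 7.2.1 limits the duty to those "that are possibly related to the study product, these should be reported as spontaneous events". No such limit is attached to SAEs during the study.
4. *Do the all-SAE rules override 7.1?* Not explicitly. Both 7.2 and SAP 6.2 start from AEs, so a site that treats 7.1 as deciding what is an AE can satisfy them while omitting unrelated worsenings.
5. *Related to what?* 7.1 does not say. 7.2.1 and Appendix 3 refer to the study or trial product.

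**Counts under each reading**

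Let k be the true number of serious worsenings in each arm (assumed equal), and q the share judged related in WMP + Rx. Neither is given in the documents.

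| Reading | WMP + Rx records | WMP records | Gap | Share of 2k unreported |
|---|---|---|---|---|
| A. Not a filter | k | k | 0 | 0 |
| B. Filter, same share q judged related in both arms | kq | kq | 0 | 1 − q |
| C. Filter, and only the trial product counts | kq | 0 | kq | (2 − q)/2 |

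The last entry in row C comes from k(1 − q) missed in WMP + Rx plus k missed in WMP, which is k(2 − q) out of 2k.

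- Row B: q = 0.25, 0.5, 0.75 leaves 75%, 50%, 25% unreported, with no gap between arms.
- Row C: q = 0, 0.25, 0.5, 0.75, 1 leaves 100%, 87.5%, 75%, 62.5%, 50% unreported.
- Row C, gap: with assumed k = 1 to 4 per planned arm of 100 and q = 0.25 to 0.75, the gap kq runs from 1 × 0.25 = 0.25 to 4 × 0.75 = 3 events. For k = 4 and q = 0.5, the table would show 2 against 0 where the truth is 4 against 4, and 6 of 8 events would be missing.

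Under-recording therefore needs one reading (the filter). A false difference between arms needs, in addition, that relatedness is judged differently by arm, with row C as the extreme.

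**The case against.** The strongest reply is that the protocol as a whole points to reading A. The 7.1 sentence says what should be reported and excludes nothing. It may simply make clear that a worsening, and not only a new event, can be an AE, so it is not true that it has meaning only as a restriction. Appendix 3 treats relatedness as something recorded about an event, not as a condition for entering it. This stands as evidence of intent, and it is why the filter reading can only be called possible. It does not remove the words from the section a site would consult first.

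The reply is also fair on the arm difference. A reader might infer that WMP would record no worsenings and that the SAE table is therefore biased against medication. The documents do not support that. It takes two readings stacked together: that the sentence is a filter, and that 'related' means only the obesity medication. The AE definition in 7.1 speaks of a pharmaceutical product or device in general, and Protocol 5.2.2.3 allows concomitant medications in both arms, so a WMP event could be judged related to something. Nor can 7.1 be read with strict literalism in one place only: the AE definition is worded for subjects who were administered a product, and read as strictly it would raise doubts about new-onset events in WMP too.

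Finally, k and q are assumed, and the percentages follow from assuming a complete filter. They show what the rule would do; they do not estimate what happened.

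**Conclusion.** Protocol 7.1 is wrong as written: its relatedness condition contradicts the definition beside it and the reporting rules around it, and following it literally would drop serious worsenings judged unrelated. An arm difference, with more lost in WMP, is possible but rests on the further step of taking 'related' to mean the trial product. The documents give no evidence that the site applied the sentence in either way, so it should not be claimed that events were omitted or that the comparison is biased.

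The size is unknown. Severity is minor: the effect is confined to worsening-type events in an untested descriptive table. The primary endpoint, the 5% significance level, the power and the efficacy analyses are untouched.

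**What to change.** In Protocol 7.1, delete the words 'and related' and add 'in both arms, regardless of causality'. This brings the sentence into line with the rest of the protocol. It costs an amendment with IRB approval (Protocol 9.1.1) and perhaps a few more SAE reports to process.

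The SAP change log covers changes since the first patient's first visit, so collection has begun and an amendment cannot recover events already left out. For those, ask the site, through the monitoring already provided for in Protocol 9.1, how it applied the sentence. If it reported all serious worsenings, nothing further is needed. If it used the sentence as a filter, or this cannot be determined, state in the report that SAEs representing worsening of a baseline condition may be under-recorded and not comparable between arms. That is one query and at most one sentence.

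SAP 6.5 needs no change, because SAP 4.1 already provides summaries by arm.
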